A meta-analysis of aspirin in eight upper GI cancer prevention cohorts has estimated cancer reduction by about 50% when compared with NSAIDs (35). In addition, combined aspirin and PPI therapy was shown in a recent model to be more effective and cheaper than any other intervention including surveillance. Early pilot data also indicates that low dose aspirin is also more effective in decreasing PGE2 levels in Barrett's patients than 25mg of rofecoxib, a selective COX-2 inhibitor (personal communication [name], USA). In a model of cancer prevention a selective COX-2 inhibitor was not as effective as a non-selective NSAID (36).

There is some controversy surrounding the potential for cardiovascular side effects of some of the COX-2 selective inhibitors in susceptible patients. Aspirin is unique in its drug group because it irreversibly inhibits platelet activity at low doses. This property explains the well-established cardioprotective properties of aspirin in at-risk individuals. Patients with BM have an increased risk of cardiovascular events. Therefore use of aspirin may be useful for secondary prevention and perhaps even primary prevention in certain at-risk groups (37). The peak incidence of Ischaemic Heart Disease (IHD) is about 10 years before the development of adenocarcinoma in Barrett's and therefore in order to both chemoprevent and cardioprotect, aspirin should be commenced in the early 50s for maximum benefit. Any NSAID drug (including the COX-2 selectives) other than aspirin would carry risks of cardiovascular complication. For this reason, together with the fact that aspirin is the best-studied anti-cancer COX inhibitor, aspirin is the drug of choice for this trial.

There is undoubtedly risk with aspirin (and without PPI) of gastrointestinal haemorrhagic complications (1-2%). But this is decreased 10 fold with PPI therapy as the damage is acid related (38, 39, 40), and still further with helicobacter pylori (HP) eradication. Indeed, aspirin may sensitise the organism to eradication therapy (41). Also, to a lesser extent, haemorrhagic stroke has also been reported. However, several reports have indicated that aspirin's advantages far outweigh any adverse effects, with major complications occurring in 0.002% and death from major complications in 0.00005% (35). While the optimal dose of aspirin for cardiac protection is probably 75mg/day, the ideal dose for chemoprevention is currently unknown and lies between 75-300mg/day.

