#### 5.1 Evaluations during the study

All patients will be followed-up annually after study entry, and an annual Follow-Up Form completed. The patients should be asked about their disease and osteoporosis status and this should be recorded on the form. The Follow-Up Site staff are reminded to:

- a) Ask patients at each follow-up visit/call about any hospital admissions or event.

AND

- b) Check patient medical records for any hospital admissions or events which should be reported as a Serious Adverse Event.

Treatment or intervention for Barrett's since the previous follow-up should also be determined and recorded along with any concomitant medication that the patient may have taken.

The Patients may be followed up by telephone or in person at year 1, 3, 5, 7 and 9 (if patients re-consented) post randomisation. A Follow-Up Form must be completed on all occasions.

At year 2, 4, 6, 8 and 10 (if patients re-consented) post randomisation (+/- 3 months either side) patients will have an endoscopy to assess their Barrett's. The following forms must be completed at these time points:

Biopsy Sampling Form

Endoscopy and Pathology Form

Follow-up Form

If the final endoscopic procedure is performed later than 8 years + 3 months (for those patients that did not re-consent to additional follow up) or later than 10 years + 3 months (for those patients who did re-consent to additional follow up), or later than 28th February 2017 (the date of LPLV) + 3 months, then provided that the patient has agreed, trial biopsy samples and trial endoscopy & pathology data will be collected.

Patients whose trial medication dose changes or is temporarily suspended (see section 8.5) should be reported using the Change of Treatment Form.

Patients who are prescribed clopidogrel should be reported using the clopidogrel CRF.

Patients who become pregnant should be reported using the Pregnancy Notification Form. Pregnant or lactating women will not undergo endoscopy and may be given dispensation to stop drug therapy for a year. This should be discussed with the Trial Office. During the first trimester only Gaviscon should be taken, after this it is advised that Omeprazole is prescribed if required. Patients may re-start esomeprazole after a break of 1 year.

Patients who undergo colonoscopy or flexible sigmoidoscopy during the trial should be reported using the Bowel Screening Form.

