#### Aspirin: Undesirable Effects

Blood and lymphatic system disorders	
Common: Increased bleeding tendencies.
 
Rare: Thrombocytopenia, agranulocytosis, aplastic anaemia.
 
Not known:

--------------------------------------	--

	Cases of bleeding with prolonged bleeding time such as epistaxis, gingival bleeding. Symptoms may persist for a period of 4–8 days after acetylsalicylic acid discontinuation. As a result there may be an increased risk of bleeding during surgical procedures. Existing (haematemesis, melaena) or occult gastrointestinal bleeding, which may lead to iron deficiency anaemia (more common at higher doses). anaemia, haemolytic anaemia, hypoprothrombinaemia, pancytopenia, occult blood loss, elevated transaminase levels
Immune system disorders	Rare: Hypersensitivity reactions, angio-oedema, allergic oedema, anaphylactic reactions including shock.
Metabolism and digestive system disorders	Not known: Hyperuricemia.
Nervous system disorders	Rare: Intracranial haemorrhage Not known: Headache, vertigo.
Ear and labyrinth disorders	Not known: Reduced hearing ability; tinnitus.
Vascular disorders	Rare: Haemorrhagic vasculitis.
Respiratory, thoracic and mediastinal disorders	Uncommon: Rhinitis, dyspnoea. Rare: Bronchospasm, asthma attacks.
Reproductive system and mammary disorders	Rare: Menorrhagia
Gastrointestinal disorders	Common: Dyspepsia. Rare: Severe gastrointestinal haemorrhage, nausea, vomiting. Not known: Gastric or duodenal ulcers and perforation which can occasionally be major (may develop bloody or black tarry stools, severe stomach pain and vomiting blood), gastrointestinal irritation (mild stomach pain), erosions, heartburn, Fatalities have occurred.
Hepatobiliary disorders	Not known: Hepatic insufficiency, hepatitis (particularly in patients with SLE or connective tissue disease)
Skin and subcutaneous tissue disorders	Uncommon: Urticaria. Rare: Steven-Johnsons syndrome, Lyells syndrome, purpura, erythema nodosum, erythema multiforme.
Renal and urinary tract disorders	Not known: Impaired renal function

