2.6.2 Blinding

After randomisation, both the patient and the treating doctor knows what treatment the patient is receiving. There is no blinding of treatments. (The cost of placebo drugs was prohibitively expensive.)

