An economic analysis will be undertaken which compares the mean per patient cost of the alternative trial arms using resource use data collected in the trial and appropriate UK unit costs. Differential costs could then be related to conversion to BA. To increase the value to decision makers, the economic data collected in the trial could be synthesised with other evidence by relating long-term (lifetime) health service costs to long-term quality-adjusted life expectancy. The analysis would be based on a state transition model, which would characterise how patients progress from BM to dysplasia and to BA competing risk of death. The annual cost and health-related quality of life associated with each stage of the disease will be estimated using trial data collected and literature. In addition, some limited data collection in appropriate non-trial patients would be undertaken. Assessments will be completed at baseline and every two years at the time of endoscopy.

- To assess whether intervention with PPI and/or aspirin induces changes in the expression of molecular markers for BA. To assess the genomics of aspirin sensitivity (efficacy and side effects)

ANALYSIS: Based on analysis of the samples, this aim will be carried out after the end of the trial under a separate analysis plan.

- To assess how quality of life is affected by the different treatments.

It was not possible to collect quality of life across time and so this secondary cannot be completed.

AspECT

A phase III randomised study of Aspirin and Esomeprazole chemoprevention in Barrett's metaplasia

Funded by CR-UK, MRC, UHL and NCI

ISRCTN No.85156844

- We will also assess what the biological risk factors are for cardiac disease and aspirin resistance.

Cardiac disease will be ascertained from SAE. The risk factors to be tested are hypercholesterol, family history of cardiac disease, patient history of cardiac disease, hypertension, diabetes or smoking. A logistic model predicting cardiac disease using these factors will be built. To consider aspirin resistance, a logistic model predicting cardiac disease in those taking aspirin will be built and described.

These 2 models will be repeated for the data from the time of the new tumour questions using cancer instead of cardiac disease.

- To assess if gender is prognostic for conversion or survival

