ANALYSIS: Using the survival time calculated for the primary objective, a logrank test to assess the effect of gender with both males and females in the sample will be reported in a table as for the primary objective. Create an AFT model looking at the gender effect adjusting for age, length of Barrett's and presence of intestinal metaplasia so that there is a time ratio with 95% confidence interval for the gender effect. Repeat with a Cox model if assumptions valid. Redo both of these models with treatment also included.

Exploratory aim

To assess aspirin's role on the development of colorectal adenomas and cancer

Use as outcome the time to colorectal cancer or colorectal adenoma. Using a logrank test, consider if aspirin use is prognostic.

To collect and bank samples for use in future ethically approved studies

To be analysed under other protocols and analysis plans.

And the exploratory uses of the data

- Describe Barrett's length over repeat biopsies and investigate a change in length from baseline to 2 years between treatment groups.

ANALYSIS: For all patients, assess if Barrett's metaplasia length shows a trend with time using repeated measures anova.

Using the baseline and 2 year length, compare the Barrett's length difference between treatment groups using paired ttest.

- Can intervention with aspirin result in a lower stage of adenocarcinoma ?
Can intervention with PPI result in a lower stage of adenocarcinoma ?

ANALYSIS: Chi square trend test on the following tables

AspECT

A phase III randomised study of Aspirin and Esomeprazole chemoprevention in Barrett's metaplasia

Funded by CR-UK, MRC, UHL and NCI

ISRCTN No.85156844

	No aspirin	Aspirin
None		
Stage I		
Stage II		
Stage III		
Stage IV		

	Low PPI	High PPI
None		
Stage I		
Stage II		
Stage III		
Stage IV		

Note: this ignores the different follow-up times

- Does adjustment for oesophagectomy, ablation therapy, endoscopic mucosal resection change the treatment effect ?

ANALYSIS: Within the multivariate AFT and COX models, add time dependent variables for the above and note the new treatment effect.

- Is the event rate different for those previous users of aspirin who were not randomised to it compared to previous users who continued with aspirin as their randomised treatment?

ANALYSIS: Kaplan-Meier curve and Logrank of the previous users of aspirin who were not randomised to it versus those randomised to aspirin.

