9.1 Resource Use and Cost Data

The health economics data for this trial will not be analysed by CSM; the analysis will be undertaken by [name].

10. Exploratory analyses not specified prior to receiving data

Any analyses not specified in this document will be exploratory in nature.

11. Serious adverse events

Serious adverse events are defined as those that are fatal, life threatening, disabling, a congenital birth defect, another important medical event which require hospitalisation or prolongation of hospitalisation. Any serious adverse event occurring whilst a participant is continuing in the study, until trial medication is stopped will be recorded. All serious adverse events will be described in tables including causality, CTCAEgrade, outcome and seriousness. A comparison of specific serious adverse events between the treatment groups (aspirin vs no aspirin and low PPI vs high PPI) will be assessed by examination of 95% confidence intervals for the difference in incidence. An overall category for any serious adverse event will also be compared using the chi square test. The analysis will be conducted by intention to treat. An overall category for renal impairment (dehydration, renal, obstruction) will be compared using the chi square test.

SAE and death major bleeds will be summed and expressed as number of major bleeds per 1000 person years. 2 major bleeds per 10000 person years is expected.

12. Data from Canada

One site in Canada ran a trial of 50 patients using the same protocol. The entire analysis plan will be re-run including this data when it is available.

AspECT

A phase III randomised study of Aspirin and Esomeprazole chemoprevention in Barrett's metaplasia

Funded by CR-UK, MRC, UHL and NCI

ISRCTN No.85156844

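### The exploratory colorectal test pools adenoma with cancer and does not check whether the aspirin arm's bowel was examined more often, so a real benefit could be attenuated or hidden

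*SAP*

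**What the plan says.** Protocol section 3 lists aspirin's role in colorectal adenomas and cancer as a tertiary/exploratory objective and gives its endpoint only as a new tumour. The SAP's whole analysis, in section 9 under the exploratory aim, is: "Use as outcome the time to colorectal cancer or colorectal adenoma. Using a logrank test, consider if aspirin use is prognostic".

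Neither the protocol's Summary Schedule of Events nor the SAP 2.8 assessment table schedules a lower-bowel examination, at baseline or later. The bowel screening form appears in the protocol schedule only among the unscheduled forms. Protocol 5.1 explains when it is used: "Patients who undergo colonoscopy or flexible sigmoidoscopy during the trial should be reported using the Bowel Screening Form". The SAP does not mention this form.

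On blinding, SAP 2.6.2 states: "There is no blinding of treatments". Protocol 10.3 lists increased bleeding tendencies with aspirin as common (1/100 to under 1/10). With frequency not known, it also lists "occult gastrointestinal bleeding, which may lead to iron deficiency anaemia".

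SAP section 7 applies intention to treat to the exploratory aims and removes PPI-only patients from the aspirin comparison. Section 9 closes by saying that the ITT sample will be used where possible. The sensitivity analyses in SAP 8.6 concern the primary aim. None deals with how colorectal lesions come to be found.

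**The concern.** An adenoma usually has to be looked for. With no scheduled examination, the time to a recorded adenoma depends on when the lesion arose and on when someone happened to look. A logrank comparison by arm is fair only if both arms are examined at similar rates. Patients and clinicians know the allocation, and aspirin has listed effects that could plausibly lead to bowel investigation, so similar rates cannot be taken for granted.

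Pooling cancer with adenoma makes this harder to see. Cancer depends less on a chance examination, but in a pooled time-to-first-event outcome it may be outnumbered by adenomas. If aspirin patients are examined more, extra adenomas found in that arm offset any real reduction. A null result could then mean no effect, or an effect masked by detection, and the planned output gives the reader no means of telling which.

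**Working it through.** **Starting figure.** The colorectal aim has no sample size, event count or power statement to reproduce. The one relevant stated quantity is the aspirin effect on colorectal cancer in SAP 2.5.1: a control-to-treated hazard ratio of 1.5, given as 33.3% effective. Inverted, 1/1.5 = 0.667, and 1 - 0.667 = 0.333, which agrees.

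**Simple approximation.** If adenomas count only when found, and detection is infrequent:

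observed ratio = true ratio × examination rate ratio (aspirin : no aspirin)

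The examination rate ratios are assumed, because the documents give none.

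| Rate ratio | Observed ratio, true 0.667 |
|---|---|
| 1.0 | 0.67 |
| 1.1 | 0.73 |
| 1.2 | 0.80 |
| 1.3 | 0.87 |
| 1.5 | 1.00 |

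The observed ratio passes 1 only when the rate ratio exceeds 1.5.

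**Simulation.** The approximation treats the whole outcome as adenoma. A simulation of onset, next examination and logrank test relaxes this. Its assumptions are not from the documents:
- adenoma onset 2% per year
- cancer 0.15% per year, found without colonoscopy
- control examination rate 2% or 5% per year
- 9 years of follow-up and a true ratio of 0.667 for both lesions
- undetected adenomas at entry equally common in both arms

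Each range below spans the two control examination rates.

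| Rate ratio | No adenomas at entry | 10% at entry | 25% at entry |
|---|---|---|---|
| 1.0 | 0.67–0.68 | 0.81–0.83 | 0.88–0.91 |
| 1.25 | 0.76–0.78 | 0.93–0.97 | 1.04–1.07 |
| 1.5 | 0.84–0.87 | 1.05–1.10 | 1.21–1.23 |
| 2.0 | 0.99–1.04 | 1.31–1.33 | 1.51–1.53 |

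With equal examination and no adenomas at entry, the test recovers the true ratio. With 2224 patients and no adenomas at entry, the chance of a significant benefit falls from 0.31–0.42 at a rate ratio of 1.0 to 0.10 at 1.5. Adenomas present at entry dilute the estimate even when examination is equal.

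**How large might the imbalance be?** Major bleeds cannot produce it. SAP section 11 says "2 major bleeds per 10000 person years is expected". For 1112 patients (half of 2224) over an assumed 9 years, that is 1112 × 9 × 2/10000 = 2.0 bleeds. For 1256 patients (about half of 2513) it is 2.3.

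Milder bleeding might matter. Suppose 1% to 10% of aspirin patients, the protocol's common band for bleeding tendencies, each had one extra examination over 9 years, against a background of 1% to 5% per year. The rate ratio is 1 + p/(9 × c), where p is that proportion and c the background rate:
- lowest: 1 + 0.01/(9 × 0.05) = 1.02
- highest: 1 + 0.10/(9 × 0.01) = 2.11

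The range runs from almost nothing to enough to abolish the effect. The documents do not narrow it.

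**The case against.** The strongest reply is that the detection imbalance is not documented. No section says that aspirin leads to colonoscopy, and none gives examination rates by arm. Occult bleeding and anaemia are listed with unknown frequency and as more common at higher doses. Every arm takes a PPI, which protocol 1.2 says cuts aspirin's gastrointestinal haemorrhage ten-fold. Some examinations may be routine screening, which need not differ by arm. All of this stands. It makes the size of the bias unknown and possibly small, but it does not supply the missing check.

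Three stronger readings are tempting and are not supported:

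- **That the test will probably reverse a protective effect.** With the SAP's own 0.667, 10% to 30% more examinations attenuates the ratio to 0.73–0.87 and does not carry it past 1. Reversal needs a rate ratio above about 1.5 by the approximation, about 2 in the simulation with no adenomas at entry, or a sizeable share of patients entering with undetected adenomas.
- **That the years before the tumour questions began are wrongly counted as tumour-free.** SAP 9 does say of two logistic models: "These 2 models will be repeated for the data from the time of the new tumour questions". It does not say that the colorectal outcome comes only from those questions. Bowel screening forms, record checks and SAE reports are other possible sources. A late start would also apply to both arms alike, so it would mainly cost events.
- **That the colorectal objective will be answered wrongly.** The documents show only that the answer may be uninterpretable.

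It is also fair to say that cancer alone is not immune. Extra colonoscopies can bring diagnosis forward, or prevent cancer through polyp removal. Cancer is less dependent on detection, not independent of it.

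**Conclusion.** The point holds as a limit on interpretation. As written, the pooled logrank test cannot distinguish fewer lesions from different intensity of looking, and the SAP plans nothing that would show whether the arms were examined equally. Under assumed increases of 10% to 30% in examinations on aspirin, a true ratio of 0.667 would appear as about 0.73 to 0.87 by the simple approximation. That is enough to hide a real benefit in an analysis with no stated power. Both the imbalance and its direction are inferred from listed side effects and open treatment, and the magnitude rests on assumed rates throughout. The aim is exploratory, and no primary or secondary conclusion depends on this test.

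**What to change.** Amend the exploratory aim in SAP section 9 as follows.

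1. State that the comparison is by randomised aspirin allocation, excluding PPI-only patients, in line with SAP section 7. The present wording about aspirin use could be read as treatment taken.
2. Report colorectal cancer and colorectal adenoma separately as well as pooled, and name cancer as the less detection-dependent result. Use NHS flagging where the patient consented, after confirming that the returns carry colorectal diagnoses, which the documents do not state.
3. Tabulate colonoscopy and flexible sigmoidoscopy rates per 100 person-years by arm from the bowel screening forms, and interpret the adenoma result in that light.
4. If adenoma yield among examined patients is shown, label it descriptive. That subset is selected after randomisation, possibly by aspirin bleeding itself, so it is not a treatment comparison.

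The cost is SAP wording and one extra table from forms the protocol already requires. The drawback is few events for cancer alone, so its confidence interval will be wide. Changing the start of time at risk is not recommended, because the documents do not show that the outcome depends on the later tumour questions.

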## 14.1 Final analysis

This trial completed recruitment within 4 years of opening to recruitment. The DSMC will decide the time point for the final analysis. Final analysis is planned 8 years after the end of patient recruitment and will be guided by the fulfilment of the sample size calculation to be when there are at least 200 events and a median of at least 5 years follow up.

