2.1 Objectives

Primary OBJECTIVES:

- To assess whether intervention with aspirin results in a decreased rate of all causes of mortality or conversion rate from Barrett's metaplasia (BM) to adenocarcinoma or high grade dysplasia.
- To assess whether high dose PPI therapy results in a decreased rate of all causes of mortality or conversion rate from Barrett's metaplasia to adenocarcinoma or high grade dysplasia.

Secondary OBJECTIVES:

- To assess whether intervention with aspirin results in decreased high-grade dysplasia, in decreased all cause mortality, in decreased oesophageal cancer incidence and in decreased cause-specific mortality when each is considered separately
- To assess whether intervention with high dose PPI results in decreased high-grade dysplasia, in decreased all cause mortality, in decreased oesophageal cancer incidence and in decreased cause-specific mortality when each is considered separately
- To assess whether there are clinical and molecular risk factors which can be identified in BM for the development of Barrett's Adenocarcinoma (BA).
- To assess the cost effectiveness of aspirin and/or PPI treatment in the prevention of BA.
- To assess whether intervention with PPI and/or aspirin induces changes in the expression of molecular markers for BA. To assess the genomics of aspirin sensitivity (efficacy and side effects)
- To assess how quality of life is affected by the different treatments.
- To assess what the biological risk factors are for cardiac disease and aspirin resistance.
- To assess gender differences in outcomes.

Exploratory aims

1. To assess aspirin's role on the development of colorectal adenomas and cancer.
2. To collect and bank samples for use in future ethically approved studies

AspECT

A phase III randomised study of Aspirin and Esomeprazole chemoprevention in Barrett's metaplasia

Funded by CR-UK, MRC, UHL and NCI

ISRCTN No.85156844

Exploratory uses of the data

1. Describe Barrett's length over repeat biopsies and investigate a change in length from baseline to 2 years between treatment groups.
2. Can intervention with aspirin result in a lower stage of adenocarcinoma ?
Can intervention with PPI result in a lower stage of adenocarcinoma ?
3. Does adjustment for Oesophagectomy, Ablation therapy, Endoscopic mucosal resection change the treatment effect ?

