2.5.3 Exploratory sample size statement October 2008

Due to protocol amendments and an expected restriction on the number of patients to be recruited, an exploratory sample size is presented at the request of the Funders. Since the trial will recruit until end Dec 2008 in the UK and possibly until the end of June in Canada rather than to the number calculated in the original sample size, this calculation should be considered as a guide to the power and treatment effect size the trial should achieve.

This exploratory sample size is calculated as per the original sample size, but with

- Annual rate of conversion of 1% (allowing for the composite primary endpoint of all cause mortality and conversion to adenocarcinoma and conversion to high grade dysplasia.)

Justification: Using the National Statistics figures for 2005 based on the age and gender structure of the first 2046 patients recruited to AspECT gives a mortality rate in a year of 1.16%.

Using the UK Barrett's conversion rate to adenocarcinoma of at least 0.98% per year without treatment for 60% of the sample and 40% with a lower conversion rate of 0.66% (due to being

AspECT

A phase III randomised study of Aspirin and Esomeprazole chemoprevention in Barrett's metaplasia

Funded by CR-UK, MRC, UHL and NCI

ISRCTN No.85156844

female, have tongues of Barrett's metaplasia or only 1cm of Barrett's, or being <45 years old. Differing rates are not published for these patients so a rate of two thirds the UK conversion rate has been used) ie 0.85% conversion rate without treatment over the whole sample.

No good estimates of rates for conversion to high grade dysplasia for the UK could be found.

In this population, it is unlikely that the event rate for the composite primary endpoint in the control arm will be less than 1%.

- HR as in colorectal cancer
- No adjustment for compliance
- the follow-up increased to 10 years

Apart from limited recruitment and checking the event rate using the age/sex structure, no information or estimates from the current trial are used.

A total of 2224 patients (196 events) (approximately 556 in each intervention group) will allow us to detect a difference in conversion rates of 0.34% per year between low dose and high dose PPI and aspirin or no aspirin. This sample size was calculated using ARTMENU in STATA release 10.0 based on the following:

- Patients will be recruited over 3 years and followed up for a further 10 years

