- Investigation of the hypothesis that aspirin will have a chemopreventive effect on all epithelial cancers using the same mechanism it does to reduce oesophageal cancer, however, high dose PPI therapy may arguably increase colon cancer incidence as gastrin levels increase and this hormone is a known stimulant for colon cancer

ANALYSIS: Define outcome as time to epithelial cancer (oesophageal, colorectal, other gi or skin). For those randomised to aspirin and low PPI or to no aspirin and low PPI, use an AFT model with stratification variables to assess if aspirin is predicting outcome.

Where possible, all these analyses will use the ITT sample.

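### Two exploratory tests in SAP section 9 do not match their questions: a paired t-test is named for a between-arm comparison, and a None-to-IV trend test is posed as a test of lower stage

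*SAP*

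**What the plan says.** **Length.** SAP section 2.1 lists as an exploratory use of the data to "investigate a change in length from baseline to 2 years between treatment groups". Section 9 takes each patient's baseline and 2-year length and compares the "length difference between treatment groups using paired ttest". The only other length analysis there is a repeated-measures ANOVA for a time trend in all patients, which makes no treatment comparison.

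**Stage.** Section 9 asks "Can intervention with aspirin result in a lower stage of adenocarcinoma", and puts the same question for PPI. The method is "ANALYSIS: Chi square trend test on the following tables". Each table has an arm per column and five rows: None, then Stages I, II, III and IV. The one caveat is "Note: this ignores the different follow-up times". On the sample, section 9 states: "Where possible, all these analyses will use the ITT sample". Patients without cancer therefore fill the None row.

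The SAP introduction says that reported results should follow this strategy and that departures must be described and justified.

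**The concern.** A paired t-test needs two measurements on the same unit. Within one arm it tests change over time. Between arms there is nothing to pair. The analyst must either run a test that does not give the stated contrast or declare a deviation.

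The stage question concerns how advanced the cancers are, but most patients in the table have no cancer. The split between None and any cancer can therefore drive the trend statistic. Fewer cancers with an unchanged stage mix could be reported as lower stage, which would repeat the incidence comparison already planned among the secondary aims. A true shift to earlier stage with equal incidence would be diluted by the None row. The SAP's caveat covers follow-up time and does not mention incidence.

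**Working it through.** **Length.** No arithmetic is needed. The question is a contrast between arms in each patient's change. The arms are independent groups, so the patient's own difference has to be compared by an unpaired method. No size is claimed for this part.

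**Stage: inputs from the documents**
- Untreated adenocarcinoma rate: "0.85% conversion rate without treatment over the whole sample" (SAP 2.5.3). Ignoring deaths, the share still in None is exp(−0.0085 × 8) = 0.934 at 8 years and exp(−0.0085 × 10) = 0.919 at 10 years.
- Planned hazard ratio of control to treatment: 1.5 (SAP 2.5.3). It was set for the composite endpoint and is borrowed here as a one-third reduction in cancers.
- Final analysis guided by "at least 200 events and a median of at least 5 years follow up" (Protocol 14.1). With the SAP's mortality rate of 1.16% and ignoring dysplasia, cancers at 200 events are about 200 × 0.85/(0.85 + 1.16) = 84.6. A split of 50 v 33 (83 in total) is close to that.

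**Assumptions.** The documents give no adenocarcinoma count by arm and no stage mix. I assumed 1,250 patients per arm, three sets of counts, and six mixes of Stages I/II/III/IV (%): 25/25/25/25, 40/30/20/10, 10/20/30/40, 50/20/15/15, 15/15/20/50 and 35/25/20/20.

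**Formula.** This is the Cochran-Armitage trend test with scores s = 0 to 4 (1 to 4 among cases only):

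z = (difference in mean score) / √{[mean of s² − (mean of s)²] × (1/n₁ + 1/n₂)}, with the means inside the root taken over both arms together.

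**Worked case A: 80 v 53 cancers, both 25/25/25/25.** Among cases the mean score is 2.5 and the mean squared score is 7.5.
- Difference: (80 − 53) × 2.5/1250 = 0.054.
- Pooled mean: 133 × 2.5/2500 = 0.133. Pooled mean square: 133 × 7.5/2500 = 0.399.
- z = 0.054/√[(0.399 − 0.0177) × 2/1250] = 0.054/0.0247 = 2.19, p = 0.029, with no difference in stage mix.

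**Simulation, identical stage mix in both arms** (40,000 trials per setting, two-sided 5%, range over the six mixes):

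| Cancers, control v treated | Expected-count p | SAP test significant | Cases-only test significant |
|---|---|---|---|
| 80 v 53 | 0.023–0.038 | 55–63% | about 5% |
| 50 v 33 | 0.072–0.101 | 38–44% | about 5% |
| 30 v 20 | 0.176–0.216 | 24–28% | about 5% |

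With equal incidence and equal mix the SAP test rejects in 4.8–5.2% of trials, so its size is correct as a test of disease burden. With 1,100 per arm the expected-count p-values barely move (0.022–0.038, 0.072–0.100, 0.175–0.216).

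**Worked case B: 80 cancers in each arm, 25/25/25/25 v 40/30/20/10.** The shifted mix has mean score 2.0 and mean squared score 5.0.
- SAP test: difference 80 × 0.5/1250 = 0.032; pooled mean 360/2500 = 0.144; pooled mean square 1000/2500 = 0.400; z = 0.032/√[(0.400 − 0.0207) × 2/1250] = 1.30, p = 0.19.
- Cases only: z = 0.5/√[(6.25 − 2.25²) × 2/80] = 2.90, p = 0.004.

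**Simulated power, equal incidence:**

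| Cancers per arm | Shift to 40/30/20/10: SAP v cases-only | Shift to 35/25/20/20: SAP v cases-only |
|---|---|---|
| 80 | 25% v 83% | 9% v 28% |
| 50 | 17% v 64% | 7.5% v 20% |
| 30 | 12% v 44% | 6.5% v 14% |

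**Other assumptions.** Taking 9 years of follow-up, 1,256 per arm and rates of 0.66% to 0.98% per year gives the same picture. With one-third lower hazard and an identical mix, the SAP test declares the treated arm lower in 61% of trials (53–67%). For the larger stage shift at equal incidence, power is 28% (23–33%) against 88% (80–92%) among cases. If the hazard is halved and the treated cancers are of later stage (25/25/25/25 against 40/30/20/10 in controls), the SAP test still declares the treated arm lower in 68% (58–74%).

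**The case against.** On length, the SAP states the right data and the right contrast. A paired test cannot be run on two arms of unequal size, so the slip would surface at analysis. That is fair, and it is why no numerical harm is claimed. The text still needs correcting.

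On stage, None can be read as the lowest category. The five-row test then compares all randomised patients and holds its size. The tables also show the Stage I to IV counts, and incidence is analysed separately, so a careful reader could see what drives a result. This stands as a reason to keep the table. It does not make the single planned p-value a test of stage.

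The numerical anchor is soft. If dysplasia were as frequent as cancer, first-event cancers at 200 events would be about 200 × 0.85/2.86 = 59. Cancers that follow dysplasia would raise the count again. The 84.6 applies the untreated rate to every arm, and 200 events is a minimum. A count of 50 in 1,250 leaves 96% in None, against about 92% from the SAP's rate at 10 years. All of this stands: the percentages are illustrations. The direction was the same in every setting tried.

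The cases-only test conditions on an event after randomisation and has low power for a modest shift. Both points stand, so it should be labelled descriptive.

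**Conclusion.** The concern holds, at minor severity. The paired t-test is the wrong method for a between-arm contrast and is probably a naming slip. The None-to-IV trend test is a valid comparison of disease burden, but alone it cannot support a claim of lower stage.

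With one-third fewer cancers and no change in stage mix, it would be significant in roughly a quarter to three-fifths of trials (24–63%) over the assumed counts. It would have 12–25% power for a large pure stage shift. These figures rest on assumed counts, arm sizes and stage mixes, and on a hazard ratio borrowed from the composite. Both analyses are exploratory, and the primary and secondary analyses are untouched.

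**What to change.** **Length.** Replace the paired t-test with ANCOVA of 2-year length on randomised treatment, adjusted for continuous corrected baseline length, age group and intestinal metaplasia. Leave out the length stratum: length is a minimisation factor, and the continuous baseline value already carries it. The other factorial treatment and sex may be added. A two-sample t-test on each patient's change is the minimal correction.

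**Stage.** Keep the five-row tables as the all-randomised comparison. Label them as overall disease burden, incidence and stage combined, and state that they are not evidence of lower stage by themselves. Add an ordinal trend test over Stages I to IV among adenocarcinoma cases, labelled descriptive because it is not protected by randomisation.

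**Cost.** A short edit to SAP section 9, with no new data. Corrected baseline length is already used in the sensitivity analyses of sections 7 and 8.6. The price of the added stage test is its low power for a modest shift: 28%, 20% and 14% at 80, 50 and 30 cases per arm.
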